#### **4.8. Biomarkers Variables**

Biomarkers to be analyzed in this study are:

- TARC
- Total serum IgE
- Immunoglobulin profiling
- Antigen-specific IgE
- Lactate dehydrogenase (LDH) [which will be measured as part of the blood chemistry]

Serum samples for measurements of biomarkers to study the PD activity of dupilumab in pediatric AD patients will be collected at time points according to [Appendix 10.2](#).

## 5. STATISTICAL METHODS

For continuous variables, descriptive statistics will include the following: the number of patients reflected in the calculation (n), mean, standard deviation, median, first quartile (Q1), third quartile (Q3), minimum, and maximum.

For categorical or ordinal data, frequencies and percentages will be displayed for each category.

All data will be summarized by 3 treatment groups (i.e. dupilumab Q2W dose, dupilumab Q4W dose and placebo). All placebo patients will be pooled for analysis regardless if it is 200 mg placebo or 300 mg placebo.

### 5.1. Demographics and Baseline Characteristics

Demographics and baseline characteristics will be summarized by treatment group for FAS. Listing of demographics and baseline characteristics will be presented.

### 5.2. Medical and AD History

Medical history will be summarized by primary SOC and PT for each treatment group. The table will be sorted by decreasing frequency of SOC followed by PT based on the overall incidence across treatment groups. Medical history will be listed.

Information on conditions related to AD includes diagnosis of AD and AD treatment history, asthma, allergic conjunctivitis, allergic rhinitis, chronic rhinosinusitis, nasal polyps, eosinophilic esophagitis, food allergy hives and other allergies due to medications, animals, plants, mold, dust mites, etc. will be summarized.

### 5.3. Pre-treatment/Concomitant Medications/Procedures

Number and proportion of patients taking prior/concomitant medications, prohibited medications and rescue medications will be summarized, sorted by decreasing frequency of ATC Level 2 and ATC level 4, based on the overall incidence for the combined dupilumab treatment groups. Patients will be counted only once for each medication class (ATC level 2 and 4) linked to the medication.

Number and proportion of patients taking prior/concomitant procedures, prohibited procedures and rescue procedures will be summarized, sorted by decreasing frequency of SOC and PT based on the overall incidence for the combined dupilumab treatment groups. Patients will be counted only once for each SOC and PT linked to the procedure.

Prior medications or procedures started before screening visit and started between screening visit and first injection date will be summarized separately.

Number and proportion of patients taking adjudicated rescue treatment (concomitant topical treatments (TCS/TCI), systemic immune-suppressants) and other treatments (emollients/antihistamines) will also be summarized separately.

Kaplan Meier curves for time to first rescue use will be generated.

The compliance of moisturizers (emollients) used from 7 days before the baseline visit to end of study, which is defined as the (number of days moisturizers used during the period) / (number of days within the period) x 100%, will be summarized by treatment group.

Listing of medications and procedures will be provided.

#### **5.4. Subject Disposition**

The following summaries by table will be provided:

- The total number of screened patients
- The total number of randomized patients: received a randomization number
- The total number of patients in each analysis set
- The total number of patients who completed the study and discontinued the study with the reason of discontinuation
- The total number of patients who completed the study treatment and discontinued the study treatment with the reason of discontinuation
- The total number of patients who continued in pediatric or adult open label extension study
- The total number of patients who entered into follow-up period and their study completion status with reason of discontinuation
- The total number of patients who entered into open-label extension study (OLE)

The following listings will be provided:

- Listing of patient disposition including: date of randomization, date of the last visit, received dose, completed study drug or discontinued by reason, completed study or discontinued by reason
- A listing of patients randomized but not treated, and patients randomized but not treated as randomized
- A listing of patients prematurely discontinued from the study or treatment, along with reasons for discontinuation
- Summary table with listing of protocol deviations will be provided

#### **5.5. Dose administration**

The compliance with study treatment will be calculated as follows:

Treatment Compliance = (Number of study drug injections during exposure period) / (Number of planned study drug injections during exposure period) x 100%

Summary of study drug administration will include the number of study drug doses administered and treatment compliance. The treatment compliance will be presented by the following specific ranges for each treatment group: <80%, and ≥80%.

Listing of dose administration: including date/time, study day, number of injections, locations of injections, dosing information, and whether or not the total dose is administered for each dose will be presented.

## 5.6. Treatment Exposure and Observation Period

The duration of treatment exposure during the study in day is calculated as:

$$(\text{Date of last study drug injection} - \text{date of first study drug injection}) + 14$$

The calculations are regardless of temporary dosing interruption. The duration of exposure during the study will be summarized by treatment group using number of patients, means, SD, minimums, medians, and maximums.

In addition, the duration of exposure will be summarized categorically by counts and percentages for each of the following categories and cumulatively by these categories as well:

≥ 14 days, ≥ 28 days, ≥ 42 days, ≥ 56 days, ≥ 70 days, ≥ 84 days, ≥ 98 days, and ≥ 112 days.

The duration of observation period during the study in day is calculated as:

$$(\text{Date of the last visit} - \text{date of the first study drug injection}) + 1.$$

The number (%) of patients with observation periods will be presented by specific time periods. The time periods of interest is specified as: < 8 days, ≥ 8 days, ≥ 15 days, ≥ 22 days, ≥ 29 days, ≥ 50 days, ≥ 57 days, ≥ 85 days, ≥ 99 days, ≥ 113 days, ≥ 141 days, ≥ 169 days, ≥ 183 days and ≥ 197 days.

## 5.7. Analyses of Efficacy Variables

For all efficacy variables, the analysis will be comparisons of each dupilumab regimen and the placebo treatment groups. The following null and alternative hypotheses for the primary endpoint will be tested for each dupilumab regimen group and the placebo group:

H0:  $p_{\text{dupilumab}} = p_{\text{placebo}}$  where  $p$  stands for the percent of responders in a treatment group

H1:  $p_{\text{dupilumab}} \neq p_{\text{placebo}}$

The analyses of efficacy variables are described in the subsections below and summarized in [Appendix 10.1](#).

Subgroups are defined by key baseline factors recorded on the CRF and listed to be considered for primary and key secondary efficacy analyses:

- Age group (≥12 to <15, ≥15 to <18)
- Sex (Male, Female)
- Ethnicity: Hispanic or Latino (no/yes)
- Race (White, Black or African American, Asian, Other)
- Duration of AD (< 13 years, ≥13 years)
- Age of disease onset (<2 years, ≥2 years)
- Age of disease onset (<5 years, ≥5 years)

- Family history of atopic disease (Yes/No)
- Baseline weight group (<60 kg, ≥60 kg)
- Baseline BMI group (overweight: ≥ 85 percentile of general population based on age and gender, < 85 percentile)  
Baseline disease severity [moderate (IGA=3) and severe (IGA=4)]
- Baseline severe EASI (<25, ≥25)
- Baseline NRS (<7, ≥7)
- Body Surface Area (BSA) (≥10% - <30%, ≥30% - <50%, ≥50%)
- Previous usage of ciclosporin (CsA) (Yes, No)
- Previous usage of methotrexate (MTX) (Yes, No)
- Previous use of systemic immunosuppressants for AD (Yes, No)
- History of asthma (Yes, No)
- History of allergic rhinitis (Yes, No)
- History of food allergies (Yes, No)

#### 5.7.1. Analysis of Primary Efficacy Variable

The Cochran-Mantel-Haenszel (CMH) test adjusted by randomization strata (disease severity (IGA=3 or 4), weight group (<60 kg or ≥60kg)) will be used for the analysis of percentage of patients with IGA 0 or 1 at week 16 or percentage of patients with EASI-75 at week 16.

All efficacy data, regardless of the patient being on the study treatment or discontinues the study treatment but remains in the study, will be used for analysis. Specifically, if a patient stays in the study until the end of the study planned placebo-controlled treatment period, all efficacy data collected up to the study planned end of treatment visit will be included in the primary analysis, regardless if the patient is on treatment or not.

#### Handling of dropouts or adjudicated rescue treatment or missing value for the binary response variables as the primary analysis

- If a patient withdraws from the study, this patient will be counted as a non-responder for the time points after withdrawal.
- To account for the impact of rescue treatment on the efficacy effect: if rescue treatment is used (see Section 4.3 for rescue treatment), the patient will be specified as a non-responder from the time the rescue treatment is used.
- If the patient has the missing value at week 16, then it will be counted as a non-responder at week 16.

The Mantel-Fleiss (MF) criterion will be performed, and if it is not met while using the option CMH (MF) in SAS procedure PROC PREQ, sensitivity analyses including each factor separately in CMH test will be conducted.

### Sensitivity analyses

1. Post-baseline Last Observation Carried Forward (LOCF) approach after censoring for rescue treatment use or study withdrawal to determine patient's status at week 16 will be conducted to assess the robustness of the primary efficacy analysis with regards to handling of missing data.
2. All observed data, regardless if rescue treatment is used or data is collected after withdrawal from study treatment will be included for analysis. Patients with missing value will be counted as non-responder.

The primary efficacy analyses will be performed on FAS, as well as on PPS as a supporting analysis.

#### **5.7.2. Analyses of Secondary Efficacy Variables**

The binary secondary efficacy endpoints will be analyzed using the same approaches as that are used for the analysis of the primary endpoints.

The endpoint "Proportion of patients with improvement (reduction) of weekly average of daily peak pruritus NRS  $\geq 4$  from baseline to week 16" will only be analyzed for patients with baseline peak pruritus NRS  $\geq 4$ . Similarly the endpoint "Proportion of patients with improvement (reduction) of weekly average of daily peak pruritus NRS  $\geq 3$  from baseline to week 16" will only be analyzed for patients with baseline peak pruritus NRS  $\geq 3$ .

The continuous endpoints will be analyzed using the multiple imputation (MI) with analysis of covariance (ANCOVA) model as the primary analysis method. Patients' efficacy data through week 16 after the rescue treatment use will be set to missing first, and then be imputed by the multiple imputation method. Missing data from the FAS will be imputed 40 times to generate 40 complete data sets by using the SAS procedure MI following the 2 steps below:

- Step 1: The monotone missing pattern is induced by Markov Chain Monte Carlo (MCMC) method in MI procedure. The monotone missing pattern means that if a patient has missing value for a variable at a visit, then the values at all subsequent visits for the same variable are all missing for the patient.
- Step 2: The missing data at subsequent visits will be imputed using the regression method for the monotone pattern with adjustment for covariates including treatment groups, randomization strata (disease severity, age group), and relevant baseline.

The week 16 data of each of the 40 complete datasets will be analyzed using an analysis of covariance (ANCOVA) model with treatment, randomization strata (disease severity, age group), and relevant baseline included in the model, and the SAS MIANALYZE procedure will be used to generate valid statistical inferences by combining results from the 40 analyses using Rubin's formula.

The imputation model will include:

- The covariates included in the ANCOVA model, including the treatment group, the baseline value and the randomization strata (disease severity, weight group)
- Measured endpoint values at every clinic visit (i.e. week 1, 2, 3, 4, 8, 12 and week 16)

Categorical variables included in above model (i.e., treatment group and randomization strata) are not expected to be missing.

To account for the impact of rescue treatment on the efficacy effect:

- Continuous efficacy endpoints: if a patient receives rescue treatment that specifies the patient as a non-responder according to the above rules for binary efficacy endpoints, the data collected after rescue treatment is initiated will be treated as missing.

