### 9.1. Statistical Hypothesis

The following null hypothesis and alternative will be tested for each dupilumab treatment group:

H0: No treatment difference between dupilumab and placebo

H1: There is a treatment difference between dupilumab and placebo

Baseline weight group (<60 kg and  $\geq 60$ kg) and disease severity (moderate [IGA=3] vs. severe [IGA=4] AD) will be the 2 stratification factors for patient randomization and will be accounted for in the statistical modeling for efficacy.

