### 9.5.2.2. Secondary Efficacy Analysis

For binary endpoints, the secondary efficacy analysis will use the same approach as that used for the primary analysis.

For continuous endpoints:

- The multiple imputation (MI) with analysis of covariance (ANCOVA) model will be used as the primary analysis method. Patients' efficacy data through week 16 after the rescue treatment use will be set to missing first, and then be imputed by the multiple imputation method. Missing data from the FAS will be imputed 40 times to generate 40 complete data sets by using the SAS procedure MI following the 2 steps below:
  - Step 1: The monotone missing pattern is induced by Markov Chain Monte Carlo (MCMC) method in MI procedure using seed number 12345.
  - Step 2: The missing data at subsequent visits will be imputed using the regression method for the monotone pattern with seed number 54321 and adjustment for covariates including treatment groups, randomization strata (disease severity, weight group), and relevant baseline.

The week 16 data of each of the 40 complete datasets will be analyzed using an analysis of covariance (ANCOVA) model with treatment, randomization strata (disease severity, weight group), and relevant baseline included in the model, and the SAS MIANALYZE procedure will be used to generate valid statistical inferences by combining results from the 40 analyses using Rubin's formula.

- To account for the impact of rescue treatment on the efficacy effect: If a patient receives rescue treatment, the efficacy data collected after rescue treatment is initiated will be treated as missing.
- In addition to the MI method described above, sensitivity analyses such as ANCOVA model with LOCF, MI method with ANCOVA model on all observed data regardless of rescue use will be conducted. Additional details on sensitivity analyses will be provided in the SAP.

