## 2. INVESTIGATIONAL PLAN

### 2.1. Study Design and Randomization

[figure not shown]
This is a randomized, double-blind, placebo-controlled, parallel-group study to investigate the efficacy and safety of dupilumab monotherapy in pediatric patients with moderate-to-severe AD. The study population will include patients  $\geq 12$  years to  $< 18$  years of age with moderate-to-severe AD whose disease cannot be adequately controlled with topical medications or for whom topical treatment is medically inadvisable (eg, intolerance, other important side effects or safety risks).

Patients who continue to meet eligibility criteria at baseline will undergo day 1/baseline assessments and will be randomized in a 1:1:1 ratio stratified by baseline weight group ( $< 60$  kg and  $\geq 60$  kg; each weight stratum will enroll approximately 120 patients) and baseline disease severity (moderate [IGA=3] vs. severe [IGA=4] AD) as follows:

- Dupilumab Q2W treatment group: Patients with baseline weight  $< 60$  kg will receive Q2W subcutaneous (SC) injections of 200 mg dupilumab following a loading dose of 400 mg on day 1. Patients with baseline weight  $\geq 60$  kg will receive Q2W SC injections of 300 mg dupilumab following a loading dose of 600 mg on day 1.
- Dupilumab Q4W treatment group: Patients will receive Q4W SC injections of 300 mg dupilumab following a loading dose of 600 mg on day 1, irrespective of weight.
- Placebo treatment group: Patients will receive placebo matching dupilumab Q2W (including doubling the amount of placebo on day 1 to match the loading dose). In order to maintain blinding for the study, patients in the  $< 60$  kg weight stratum will receive, in a 1:1 ratio, either placebo matching 200 mg dupilumab (including doubling the amount of placebo on day 1 to match the loading dose) or placebo matching 300 mg dupilumab (including doubling the amount of placebo on day 1 to match the loading dose). In the  $\geq 60$  kg weight stratum, the patients randomized to the placebo group will receive placebo matching 300 mg dupilumab (including doubling the amount of placebo on day 1 to match the loading dose).

In order to maintain blinding, all patients will receive an injection Q2W from day 1 to week 14. Patients will receive placebo injection at the weeks dupilumab is not given.

Below diagram shows the planned number of patients in each dose group.

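### SAP 5.7.2 twice names age group as a randomization stratum in the model for the continuous secondary endpoints; the stratum is weight group

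*SAP*

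**What the plan says.** SAP 5.7.2 spells out the randomization strata three times in its account of the multiple-imputation ANCOVA, and the three do not agree.

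- Imputation step 2 adjusts for "covariates including treatment groups, randomization strata (disease severity, age group), and relevant baseline".
- The week-16 analysis sentence uses a "model with treatment, randomization strata (disease severity, age group), and relevant baseline included in the model".
- The bullet that then lists what the imputation model contains describes the ANCOVA covariates as "including the treatment group, the baseline value and the randomization strata (disease severity, weight group").

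The rest of the plan names one pair of factors. SAP 2.1 has patients "randomized in a 1:1:1 ratio stratified by baseline weight group" and disease severity. Protocol 9.1 says that weight group and disease severity "will be the 2 stratification factors for patient randomization and will be accounted for in the statistical modeling for efficacy". SAP 5.7.1 uses a CMH "test adjusted by randomization strata (disease severity (IGA=3 or 4), weight group" for the primary endpoint.

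**The concern.** The two sentences name a factor that was not used in the randomization and leave out one that was. They belong to the primary method for every continuous secondary endpoint, so this is operative text.

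Age group is also a real variable in the SAP: a demographic grouping in 4.1 and a subgroup factor in 5.7. A program that followed the sentence literally would run without an error message.

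Three things would follow from the literal reading:

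- The ANCOVA would omit a stratification factor, contrary to the commitment in Protocol 9.1.
- The main analysis would differ from its LOCF and WOCF sensitivity analyses in a covariate as well as in missing-data handling, because those analyses refer to the randomization strata without listing them.
- Ranks 3 and 4 of the testing order, which gate every later test, would rest on a model other than the one in the protocol.

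**Working it through.** **1. The texts side by side**

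| Place | Second stratum named |
|---|---|
| Protocol 3.1, 5.5, 9.1; SAP 2.1, 2.3 (design) | weight group |
| SAP 5.7.1 (CMH) | weight group |
| Protocol 9.5.2.2, step 2: "covariates including treatment groups, randomization strata (disease severity, weight group), and relevant baseline" | weight group |
| SAP 5.7.2, step 2 | **age group** |
| Protocol 9.5.2.2, week-16 ANCOVA: "model with treatment, randomization strata (disease severity, weight group), and relevant baseline included in the model" | weight group |
| SAP 5.7.2, week-16 ANCOVA | **age group** |
| SAP 5.7.2, imputation-model bullet | weight group |

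The two SAP sentences follow the protocol's sentences closely, with the one term changed. SAP 1.2.3 lists a single modification, which concerns an adverse-event definition. Nothing suggests a deliberate change.

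The two sentences differ in one respect. Step 2 introduces its list as non-exhaustive, so a model with both age and weight could satisfy it. The ANCOVA sentence has no such latitude.

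**2. Reach**

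From the hierarchy table in SAP 5.7.2, the continuous endpoints are:

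- Q2W: ranks 3, 4, 19–24 and 33, which is 2 + 6 + 1 = 9
- Q4W: ranks 11, 12, 27–32 and 35, which is 2 + 6 + 1 = 9

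The total is 18 of 40. It includes ranks 24 and 32 (week-4 percent change in pruritus), which come under the same method although the ANCOVA sentence speaks of week 16.

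**3. Loss of precision under the age reading**

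The documents give no covariate effects, so these are assumptions. Let R² be the share of residual variance explained by weight group (0–0.10) and r the correlation between age group and weight group (0–0.7). Age recovers R²r² of that variance, so

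SE(age) / SE(weight) = √[(1 − R²r²) / (1 − R²)]

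| R² | r = 0 | r = 0.5 | r = 0.7 |
|---|---|---|---|
| 0.02 | 1.010 | 1.008 | 1.005 |
| 0.05 | 1.026 | 1.020 | 1.013 |
| 0.10 | 1.054 | 1.041 | 1.028 |

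For example, with R² = 0.10 and r = 0, √(1/0.90) = 1.054.

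**4. Simulation**

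The set-up was complete data without imputation, 3 × 80 patients, 40:40 by weight in each arm, severe share 30%, 50% or 70% (assumed), R² of 0 or 0.10, and 20,000 replicates per cell.

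- SE ratio at R² = 0.10: 1.057, 1.043 and 1.029 for r = 0, 0.5 and 0.7
- SE ratio at R² = 0: 1.001–1.002
- Type I error: 4.7–5.2% with weight, 3.8–5.1% with age

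**5. Power**

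The SAP gives planning rates only for binary endpoints. Converted by probit difference (assuming normal outcomes with equal variance), they imply 0.79 to 1.08 SD. The smallest comes from IGA 29% versus 9%: −0.553 − (−1.341) = 0.79.

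At 0.787 SD with 80 per arm and 234 degrees of freedom, analytic power over R² from 0 to 0.10 is 99.86–99.95% with weight and 99.86–99.91% with age. In simulation the two models gave opposite verdicts in at most 0.07% of trials.

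For a smaller effect, take 0.4 SD (assumed), R² = 0.10 and r = 0. The standardized difference is 0.4 × √(80/2) = 2.53 with age and 2.53/√0.90 = 2.67 with weight. By the normal approximation, power is Φ(2.53 − 1.96) = 71.6% versus Φ(2.67 − 1.96) = 76.0%.

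**The case against.** The strongest reply is that nobody would be misled. Both sentences use the term randomization strata, which the design defines without ambiguity, and the bullet below them sets out the ANCOVA covariates with weight group. A programmer meets both lists within a few lines and would ask. On that view this is a copy-edit, and consequences drawn from the literal reading are speculative.

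Most of that stands. The intended model is recoverable, and silent misprogramming is a possibility, not a prediction. It does not make the text right. Two of the three statements of the strata in the governing section are wrong, and a pre-specified model should have one reading.

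Two narrower points also have force.

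- The ANCOVA sentence refers to week-16 data, so on its exact words it covers 16 ranked tests; 18 is the count for the method as a whole.
- The reassuring power figure comes from binary planning rates. The documents give no effect sizes for BSA, SCORAD, CDLQI, POEM or HADS, which make up 10 of the 18 tests (19–22, 33, 27–30, 35). That figure should not be carried over to them. The 0.4 SD example shows that a loss of a few points of power is possible there under the least favourable assumptions tried.

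**Conclusion.** The concern holds and is minor. SAP 5.7.2 contradicts the randomization, the protocol's version of the same sentences, SAP 5.7.1 and its own bullet.

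The comparison stays valid under either reading; adjusting for age in place of weight is at most slightly conservative. The cost would be precision, and only if weight predicts outcome after adjustment for baseline and severity, which the documents do not address. Over the assumed ranges the standard error is about 0–6% larger. At effects of 0.79 SD or more, power stays at 99.8% or higher under both readings. The effect on the imputation itself was not simulated.

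The primary endpoint, EASI-75 and the two pruritus responder endpoints are analysed by CMH and are not affected.

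**What to change.** In SAP 5.7.2, replace age group with weight group in imputation step 2 and in the week-16 ANCOVA sentence. Both then agree with the bullet below them, SAP 5.7.1, and Protocol 9.1 and 9.5.2.2. No entry in SAP 1.2.3 is needed, because the change restores the protocol's model. The cost is one word in each of two sentences before database lock, with no effect on trial conduct.
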